5. STATISTICAL ANALYSIS
6. ETHICAL CONSIDERATIONS
7. BIBLIOGRAPHY

1. INTRODUCTION

Breast cancer (BC) is the most frequently diagnosed malignant tumor in women regardless of the country's level of development. In 2018, at a European level it accounted for approximately 28% of the total cancers diagnosed in this sex¹ and, specifically in Spain, the estimated incidence that same year was 101/100,000 women¹.

The scientific advances that have occurred in recent years have improved its prognosis. Screening or early detection strategies have notably contributed to this evolution for some age groups and the elderly. Knowledge of risk factors by the population^{2,3}.

However, it is necessary to take into account that some screening methods have side effects and that they can act to the detriment of detection early^{4,5}. On the other hand, there is abundant literature that reveals the relationship of various biological, behavioral and environmental factors in the development of CM⁶⁻⁶⁶. Specifically, in the case of behaviors, making women aware of their influence makes it possible for them to establish preventive measures^{67,68}.

Additionally, it is worth noting the individualized estimates of the risk of developing CM⁶⁹. According to Shiek et al.⁷⁰ these can contribute to less testing, a lower number of false positives, and fewer treatments. At present, there are algorithms that have been designed to estimate the probability of developing BC. Its use makes it possible to determine which risk reduction options are most effective in preventing its development^{68,71}. One of the first and most popular is the one developed by Gail et al.⁷². Subsequently, validations were carried out to adjust the risk to specific conditions⁷³. Although its validity has been demonstrated for estimations population, it seems to be limited for individualized estimates⁷⁴. The parameters that it includes in its current version are the age of the woman (from 35 years), age of the first period, age of the woman in which her first child was born (in the case of having them), number of relatives of first degree cancer, number of previous biopsies, and race. Despite its effectiveness, some authors point out the need to continue with research that allows the development of more specific tools⁷⁵.

On the other hand, the use of technology is becoming a common channel of communication, from a care perspective, between the population and healthcare personnel. There are even terms to refer to it specifically. For example, eHealth or the use of information and communication technology in the field of health and, more specifically, mHealth as the use of mobile devices in the field of health ^{76,77}.

The Internet is a great source of information used by between 30 and 50% of patients to seek information about their illness⁷⁸. The fact that patients are well informed and understand the process of their disease contributes to improving their relationship with healthcare personnel and who adopt a more active role in their health ^{78,79}. Although these means make it possible for patients to have accessible information quickly and permanently, it must not be forgotten that the absence of quality criteria in some sources available online can work against it and this justifies the need to help patients to discriminate what information is correct, truthful and appropriate to the characteristics of each one.

In this sense, it should be noted that there is beginning to be evidence that includes the benefits and ways of using web-apps as means to get people to modify risky behaviors and/or acquire healthy behaviors to prevent pathologies such as overweight, diabetes and the cancer ^{80,81}.

2. JUSTIFICATION

The use of digital media, such as a web-app, to publicize MC risk factors makes it possible to specifically establish measures aimed at reducing its prevalence, which in turn will contribute to reducing the number of cases of CM.

On the other hand, making women aware of their BC risk factors, as well as quantifying the risk of developing the tumor, is useful for them to be aware of the magnitude of the problem and take steps to minimize your risk.

Since there is no digital strategy in Asturias that informs and reduces the risk of developing breast cancer, through the modification of the main risk factors, in young women, the present study has been proposed with the objectives indicated below. continuation.

3. HYPOTHESIS AND OBJECTIVES

Based on the reviewed bibliography, it can be affirmed that establishing measures that contribute to improving knowledge related to the prevention of a health problem and help to perceive the risk of developing said problem, contribute to increasing the development of preventive behaviors.

3.1. Hypothesis

The hypothesis that this study will try to demonstrate is that an educational intervention, based on the use of a web-app, will be effective in improving knowledge and risk behaviors for breast cancer in women between the ages of 25 and 45, residents in health area 7 of the Principality of Asturias.

3.2. Objectives

3.2.1. Main Objetive

To evaluate the effectiveness of an educational intervention for the prevention of breast cancer risk through the use of a Web-App in women residing in health area VII of the Principality of Asturias.

3.2.2. Specific Objetive

- Evaluate adherence to behavioral recommendations before and after after the educational intervention for each group separately.
- To compare adherence to behavioral recommendations after the intervention between the intervention and control groups.
- Evaluate, in each group separately, the knowledge in relation to the risk factors and symptoms of breast cancer before and after the intervention.
- To compare the level of knowledge in relation to the risk factors and symptoms of breast cancer between the intervention and control groups before and after the intervention.
- Estimate the risk and self-perception of developing breast cancer before and after the intervention for each of the groups.
- To compare the risk and self-perception of developing breast cancer between the intervention and control groups after the educational intervention.

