4.2. Study population

It will be made up of women belonging to the VII health area of the Principality of Asturias, aged between 25 and 45 years, without a previous diagnosis of BC.

All women who give written consent to participate in the study will be included. Those who: (i) do not have adequate physical or psychological characteristics to participate in the study will be excluded; (ii) do not have the means to regularly access the web-app that will be used to carry out the educational intervention; (iii) your contact by email is not possible.

The recruitment of women will be carried out, between the months of January and February 2022, by sending a letter of invitation to participate from the health area. A random sample of 361 women will be sufficient to estimate, with 95% confidence and an accuracy of +/- 5 percentage units, a population percentage that is expected to be approximately 75%. The percentage of necessary replacements has been predicted to be 20%.

The health area VII technician and member of the research team ([name]) will draw up a list of all the women likely to be included in the study. The members of the research team prepare a letter for each of the women and they will be sent from the management of Sanitary Area VII to the women by postal mail.

The letter contains a contact email to which they will write if they are interested in participating. The women will be answered as the emails are received and when we have obtained the necessary sample, the project will be explained in detail with an information sheet that they may have at their disposal and they will be given their consent informed, which they will sign by selecting the box "I wish to participate voluntarily" that will appear at the end of the consent. Finally, they will be asked for a username and password to access the web-app. In other words, the user or pseudonym to access the web-app will be selected by the woman herself.

The selected women will be distributed, in March 2022, between the intervention (IG) and control (CG) groups using the simple randomization method and with a 1:1 ratio.

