4.3. Data collection: tools and procedure

The data collection will take place during the months of March (pre-test) and June 2022 (post-test). At both times it will be done virtually, using a digital form. Participants will access this form through the project's web-app. The pre-test collection will be carried out after signing the consent and the post-test, after the educational intervention, that is, at 12 weeks.

At both moments, information will be collected related to personal, anthropometric, and behavioral variables (diet and physical activity), self-examination, knowledge related to risk factors and symptoms of breast cancer, perception of risk of developing breast cancer, and barriers to carry out. take actions to prevent it.

Additionally, after the educational intervention, satisfaction with the use of the web-app will be evaluated.

The information on the behavioral variables will be recorded using the Motiva.Diaf questionnaire. It includes 12 items that measure adherence to and motivation to carry out recommendations related to nutrition (questions 1 to 7) and physical activity (questions 8 to 12). Each item presents a Likert-type response format with a range from 0 (lack of motivation to make the recommendation) to 5 (intrinsic motivation). In addition, each separate recommendation can be interpreted dichotomously (makes=1 or does not make the recommendation=0). Finally, the synthetic variable adherence to healthy recommendations is elaborated as a result of scoring each item in its dichotomous interpretation (range 0=worst adherence to healthy recommendations to 12=greatest adherence to healthy recommendations).

The self-examination is carried out by means of the question, do you perform the breast self-examination once a month.

The information related to knowledge, risk perception and barriers with the MARA questionnaire. This questionnaire, specifically related to breast cancer, consists of 31 items that measure the following constructs: knowledge related to risk factors (9 items), knowledge related to signs and symptoms (9 items), perception of risk of developing breast cancer breast (6 items) and perceived barriers to carry out prevention strategies (7 items). Items related to knowledge have a score of 0 (error) and 1 (correct), therefore the range of scores, both for risk factors and for signs and symptoms, is between 0 and 9. The score of the other two scales is represented on a Likert-type scale ranging from 1

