5. STATISTICAL ANALYSIS

Initially, the normality of the distribution of the variables will be verified, the Kolmogorov-Smirnov test will be used. A description of the variables will be made using percentages, means (standard deviation) or median (interquartile range) depending on their nature and distribution.

To determine the association between variables, the chi-square test, McNemar for qualitative variables, will be used. For qualitative variables, they will be determined based on the distribution of variables.

Linear regression analyzes will be carried out to determine which variables best predict the score after the intervention in terms of knowledge about risk factors, signs-symptoms of early detection of breast cancer, knowledge and adherence to healthy behaviors.

The analyzes will be carried out using the IBM SPSS version 24.0®, considering that the results were statistically significant when the value of p is ≤ 0.05 .

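### Specific objective 4 compares knowledge between the randomised groups at pre-test, while section 5 specifies no 12-week group comparison adjusted for the pre-test score (minor; free to improve)

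*Combined protocol and SAP*

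**What the plan says.** Section 3.2.2 lists six specific objectives, three of which compare the groups with each other. The knowledge objective (the fourth) makes that comparison "between the intervention and control groups before and after the intervention". The other two look only at the later time point: "To compare adherence to behavioral recommendations after the intervention between the intervention and control groups" for adherence, and "between the intervention and control groups after the educational intervention" for risk and self-perception.

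Section 4.2 forms the groups "using the simple randomization method and with a 1:1 ratio", in March 2022, and states no stratification. Section 4.3 places the pre-test in March 2022 as well, after consent, and the post-test at 12 weeks. It does not say whether the pre-test comes before or after allocation. Knowledge is scored as two scales, risk factors and signs and symptoms, each from 0 to 9.

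Section 5 names tests in general terms: "To determine the association between variables, the chi-square test, McNemar for qualitative variables, will be used". It ties no test to any objective. The threshold is also general, "considering that the results were statistically significant when the value of p is ≤ 0.05", with no exception for baseline comparisons. The linear regression is described as a search for the variables that best predict the post-intervention score. It is not described as an estimate of the group effect with the pre-test score as a fixed covariate.

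**The concern.** In a randomised trial, the arms differ before the intervention only by chance, provided that the baseline is measured before allocation or is not affected by it. A significance test of that difference therefore answers no scientific question. If significant, it is a chance finding. If not significant, it does not show that the arms are close.

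The useful role of the pre-test score is as a covariate in the 12-week comparison, where it removes the effect of chance imbalance and sharpens the estimate. The plan collects the score and makes its between-group comparison an objective, but does not commit to this use. Baseline is also handled differently across outcomes, since only knowledge has a between-group comparison at pre-test. Knowledge is named in the hypothesis (section 3.1), so the point touches a central outcome.

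**Working it through.** **Inputs from the protocol.** Expected percentage 75%, precision ±5 points, 95% confidence, 20% replacements and n = 361 (section 4.2); two knowledge scales (section 4.3); p ≤ 0.05 (section 5). **Assumptions.** Two-sided testing, scores in SD units because no SD is given, arms of equal size, and a pre-post correlation r of 0.5 to 0.7 because none is given.

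**1. The plan's own figure.** n = 1.96² × 0.75 × 0.25 / 0.05² = 288.1. Allowing for 20% loss, 288.1 / 0.80 = 360.1, rounded up to 361. The stated figure reproduces. It implies about 361 / 2 ≈ 180 women per arm at randomisation and 361 × 0.8 / 2 ≈ 144 per arm after the predicted loss.

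**2. False alarms at pre-test.** Each test has a 5% chance of significance when the null is true. For at least one of two scales, the chance is 5% if they are perfectly correlated and 1 − 0.95² = 9.75% if they are independent.

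**3. What a non-significant result leaves open.** The largest gap that is still non-significant is 1.96 × √(2/n per arm):
- 180 per arm: 1.96 × √(2/180) = 0.207 SD
- 144 per arm: 1.96 × √(2/144) = 0.231 SD

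A real imbalance of 0.20 SD would be flagged only 48% of the time with 361 women and 40% with 288.

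**4. Effect on an unadjusted post-test difference.** A pre-test gap carries over in proportion to r.

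| Per arm | Gap at the limit | Shift, r = 0.5 | Shift, r = 0.7 |
|---|---|---|---|
| 180 | 0.207 SD | 0.103 SD | 0.145 SD |
| 144 | 0.231 SD | 0.116 SD | 0.162 SD |

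**5. Type I error.** Given a standardised pre-test difference z, the unadjusted post-test statistic under no effect has mean r·z and variance 1 − r². Conditional type I error:

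| z | r = 0.5 | r = 0.7 |
|---|---|---|
| 1.95 (just non-significant) | 12.8% | 20.2% |
| 1.0 | 4.8% | 3.9% |

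Averaged over all possible imbalances, the rate is 5%.

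**6. What adjustment gains.** Relative to comparing raw post-test scores, adjustment multiplies the variance of the group difference by 1 − r², which is 0.75 at r = 0.5 and 0.51 at r = 0.7. With 144 per arm, the difference detectable with 80% power is 2.802 × √(2/144) = 0.330 SD unadjusted. Adjusted, it is 0.330 × √0.75 = 0.286 SD or 0.330 × √0.51 = 0.236 SD.

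**The case against.** The strongest reply is that the baseline significance test is itself an inference. The objective says only that knowledge will be compared, section 5 assigns no test to it, and a table of pre-test scores by arm would satisfy it. That stands, so the false-alarm argument is conditional on a test being run. The wording might also have meant change compared between arms, but it does not say so, and no such model is specified.

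Four stronger readings are tempting, and the documents do not support them.
- A reader might infer that a non-significant pre-test result will be used to justify comparing raw post-test scores, or to decide whether to adjust. The plan states no such rule.
- A reader might infer that the 18 knowledge items will be tested one by one. Section 4.3 scores two scales and plans no item-level tests.
- A reader might take it as settled that any pre-test difference is chance. Allocation and pre-test both fall in March 2022 and their order is not stated. If women knew their group before the pre-test, differential completion could produce a real difference.
- A reader might infer that the 12-week comparison is biased or that its error rate is inflated. A baseline test does not alter the post-test estimate, and the unadjusted comparison keeps its overall 5% error.

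It is also fair that step 4 of the working takes the most extreme gap that remains non-significant. The chance SD of the gap with 144 per arm is √(2/144) = 0.118 SD, so a gap of that ordinary size would shift the raw difference by 0.118 × 0.5 = 0.059 to 0.118 × 0.7 = 0.083 SD.

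What survives is that a pre-test group comparison is a stated objective, the threshold exempts nothing, and no baseline-adjusted group effect is specified.

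**Conclusion.** The point holds as a minor one. The pre-test comparison in objective 4 is uninformative if tested, and the plan leaves unused the analysis that would put the pre-test score to work. The consequence is lost precision and exposure to whatever imbalance chance produces; the 12-week result is not invalidated.

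The false-alarm figure depends on a test being performed and on a pre-test that allocation cannot have influenced. The sizes of the shift and of the precision gain depend on the assumed correlation of 0.5 to 0.7 and would be smaller if the true correlation is lower.

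**What to change.** - Reword objective 4 to compare knowledge between groups at 12 weeks, adjusted for the pre-test score.
- Add the model to section 5: ANCOVA, or equivalently linear regression, of the 12-week score on group and pre-test score, both kept in the model whatever the data show. Keep it separate from the predictor-seeking regression.
- Apply the same adjustment to the adherence and risk-perception comparisons, so that baseline is handled alike across outcomes.
- Report pre-test scores by arm as description (mean and SD, or median and interquartile range), without p-values.
- State whether the pre-test precedes allocation.

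The cost is rewording the between-group objectives and a short model specification in section 5. The pre-test scores are already collected, and the sample size of 361 does not change.

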(totally disagree) to 5 (totally agree), the total perception score being between 6 and 30 points (the lower the score, the lower the perception of risk and the barriers between 7 and 35 points (the lower the score, the fewer perceived barriers).

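### Do the fifth and sixth specific objectives promise a breast-cancer risk outcome that the plan never defines?

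*Combined protocol and SAP*

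**What the plan says.** Two of the six bullets in section 3.2.2 concern risk. The fifth reads "Estimate the risk and self-perception of developing breast cancer before and after the intervention for each of the groups" and the sixth "To compare the risk and self-perception of developing breast cancer between the intervention and control groups after the educational intervention". Section 2 (Justification), speaking of making women aware of their risk factors, adds "as well as quantifying the risk of developing the tumor" as something useful to them.

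Section 4.3 describes the measurements. It opens with "At both moments, information will be collected related to personal, anthropometric, and behavioral variables (diet and physical activity), self-examination" and goes on to knowledge, risk perception and barriers. The source for these last three is given as "The information related to knowledge, risk perception and barriers with the MARA questionnaire", with "the total perception score being between 6 and 30 points". Nothing in the section is described as an estimated probability of disease.

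Section 5 plans linear regressions for the post-intervention score "in terms of knowledge about risk factors, signs-symptoms of early detection of breast cancer, knowledge and adherence to healthy behaviors". Neither perceived nor estimated risk is on that list.

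One risk algorithm has its inputs set out, and only in section 1 (Introduction), as background: "The parameters that it includes in its current version are the age of the woman (from 35 years), age of the first period", followed by reproductive history, affected relatives, biopsies and race. No later section adopts it.

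**The concern.** Read literally, the two bullets name two quantities, a risk and a self-perception, and the methods provide only the second. An outcome promised in the objectives but not defined in the methods is either dropped without comment or constructed once the data are in hand.

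The second possibility is the more serious. If someone later applied an algorithm like the one in section 1, the result would say little about the web-app. None of its listed inputs is a diet, activity or knowledge variable, so 12 weeks of education could hardly move it. A difference between arms would then reflect chance imbalance or uneven drop-out, yet it could be reported as an effect on cancer risk. The algorithm also starts at age 35, while section 4.2 enrols from 25.

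**Working it through.** The point is mainly one of wording, so the check sets the sections side by side and adds the little arithmetic that applies.

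1. **Objectives affected.** Section 3.2.2 has six bullets: two on adherence, two on knowledge, two on risk and self-perception. At most one component of 2 of the 6 lacks a measure.

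2. **What MARA contains.** Section 4.3 gives 9 risk-factor items, 9 sign-and-symptom items, 6 perception items and 7 barrier items: 9 + 9 + 6 + 7 = 31, the stated total. Every item is accounted for, so no estimated-risk item sits inside the questionnaire. The perception range is 6 × 1 = 6 to 6 × 5 = 30, as stated. The perceived-risk half is therefore fully specified and collected at both times.

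3. **What else is collected.** The adherence score (0 to 12), one self-examination question, satisfaction with the web-app (post-test only), and personal and anthropometric variables that are not itemised. Some of these could feed a risk model, but the text links them to none. Because anthropometric, diet and activity data are taken at both times, the text also does not show that any model used would rest on fixed inputs alone.

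4. **What section 5 shows.** Its regression list leaves out estimated risk, but also perceived risk, barriers and self-examination, all of which section 4.3 measures. Absence from that list is therefore no evidence about risk in particular. Only the absence from section 4.3 carries weight.

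5. **Whether any figure depends on it.** The plan's sample size reproduces as a precision calculation: n = z²p(1 − p)/d² = 1.96² × 0.75 × 0.25 / 0.05² = 288.1. Allowing for 20% replacements, 288.1 / 0.80 = 360.1, rounded up to 361. The calculation concerns a single percentage and contains no risk outcome, effect size or standard deviation. Defining or removing an estimated risk would leave it unchanged.

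6. **The age mismatch.** Completed years 25 to 45 are 21 single-year ages, of which 25 to 34 are 10, so the section 1 algorithm would not cover 10 of the 21. The documents do not give the age mix, so this is not a share of participants. It describes a tool that the plan does not use, and it is not counted in the size of the problem.

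**The case for a change.** The strongest argument for a change is that the two-quantity reading has support outside the objectives. Section 1 spends a paragraph on individual risk estimation, section 2 treats quantifying risk as distinct from awareness of risk factors, and the main objective in section 3.2.1 speaks of preventing breast-cancer risk. Against that background a perception result could be presented as a risk result, and perception is no substitute: education may raise perceived risk while actual risk stays the same. Rewording two bullets would cost almost nothing.

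Part of this stands. The text is ambiguous, and no section settles it. But the sentence in section 2 gives quantification a purpose of informing women, not of serving as a trial endpoint. The English also reads as a rough translation: breast cancer is abbreviated as BC, CM and MC, and section 5 mentions qualitative variables twice where the second mention is probably meant to be quantitative. A compressed rendering of self-perceived risk is quite plausible. The harm described needs a further step that the plan does not take, namely choosing a model afterwards and reporting its output as an effect. A low cost of rewording is not a reason for it when no planned result would differ.

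**Conclusion.** The wording gap is genuine, but it is missing detail with no gain from filling it. It affects at most one component of 2 of 6 specific objectives. If the bullets mean self-perceived risk, the MARA perception score answers them. If they also mean an estimated risk, the plan defines no such quantity, and the sensible reading is to analyse perceived risk and draw no conclusion on cancer risk itself.

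The hypothesis in section 3.1 is about knowledge and risk behaviours, and the section 5 regressions target knowledge and adherence. Those results, and perceived risk, are the same either way. No figure for harm can be given, because any such figure would rest on an algorithm that the plan does not adopt.

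The conclusion assumes that no estimated-risk effect is reported as a planned result. If one were, it should be read as exploratory, since this plan gives it no model, inputs or time horizon.
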